This training manual is to serve as a detailed guide for the survey laboratory personnel who will be recruited for sample collection, processing and laboratory analysis. The manual provides detailed methodology for field procedures, including universal precautions, labeling, specimen collection and processing, sample storage and transportation, and management of the cold chain. This guide should be read carefully prior to the field work, and any questions should be discussed with the survey coordinator, principal investigators, laboratory coordinator and CDC technical support team.

There will be one survey team, consisting of one supervisor, four interviewers, and four lab technicians. The study will consist of 55 villages (clusters) and 21 households will be visited per village to recruit one non-pregnant woman aged 18-49 years per household for a total of 790 participants. Each survey team will visit one village per day to interview 21 women each. After

interviewers complete the questionnaire, a lab technician will collect blood after informed consent. Two lab technicians will carry out blood collection into pre - labelled vacutainers (two purple-top and one yellow-top) after verification of the participant. After completion of blood collection from about 12 participants (approximately 3-4 hours), blood specimens will be transported to Morogoro processing laboratory. There, specimens will be processed, aliquoted and stored according to the details given below on the same afternoon. Twice a week the specimens both refrigerated and frozen, will be transported maintaining the appropriate cold chain requirement to the TFNC in Dar-Es-Salaam for laboratory analysis by various biochemical tests. Arrangements for sample collection for the next day should be completed the previous afternoon by the laboratory personnel.

Biomarker	Condition or nutrient
Hemoglobin	Anemia
Erythrocyte folate	Folate
Serum folate	Folate
Serum vitamin B12	Vitamin B12
Serum ferritin	Iron
Soluble transferrin receptor	Iron
Alpha 1 acid Glycoprotein	Inflammation
C-reactive protein	Inflammation
Retinol Binding Protein	Vitamin A
Retifior Diffaing Frotein	
MTHFR	Folate/one-carbon metabolism
Homocysteine	Vitamin B12 and folate

Table 1: Baseline Biomarker Assessment: Laboratory Analyses and Indicators

Overall Universal Precautions and Considerations

- Collection, testing, and processing of biological specimens are critical parts of the Micronutrient Survey.

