Figure 5: Portable freezer/Cold Box for ease of transportation of samples to MPL and frozen samples to TFNC.

Items to be taken to the field for EACH survey teams. Complete list of supplies to be taken by each team for specimen collection of 21 women is given in Annexure 3 **Specimen processing and storage at MPL:**

Kindly ensure ACCURATE LABELLING of all samples.

After the samples are brought to the NPL, one of the EDTA vacutainers will be tested for automated blood cell counts in the Automated Blood Cell Counter. Any subject found to be anemic will be tested for the manual reticulocyte count.

The second EDTA tube will be used for red cell folate analysis for which 100 \Box 1 EDTA blood will be transferred after gently mixing to two plastic cryovials which contains 1 ml of 1% ascorbic acid solution. The pipette tip will be rinsed a few times in the ascorbic acid solution to ensure quantitative transfer of the EDTA blood. It is critical that the pipetting is done accurately. This vial should be labeled and stored at -20°C.

The leftover sample will be spun for plasma separation at low speed and plasma will be transferred in two cryovials for plasma homocysteine. Samples will be stored at -20° C at NPL.

Note: At room temperature there is an increase in HCY of about 10% per hour! Therefore it should be ensured that the sample processing is performed as soon as possible.

For serum separation, the clotted blood sample will be centrifuged at 1000 g for 10 minutes. Serum will be aliquoted ($300\square1$ each) into four plastic cryovials and one PCR vial: for Vitamin B12, retinol, folate and a backup vial. PCR vial for [name] (Germany) needs and aliquot of ~100 ul serum for ferritin, sTfR, CRP, AGP, and RBP.

Samples	Biomarker	Storage Conditions
K ₂ EDTA 1 st vacutainer	Hemoglobin	4ºC
	Reticulocyte count (if necessary)	
	DNA extraction for MTHFR	
K ₂ EDTA 2 nd vacutainer	1. RBC folate	-20°C
	2. Back up for whole blood folate	
	3. Plasma for homocysteine	
	4. Back – up vial for Plasma	
Yellow capped vacutainer	1. Serum folate	-20°C
	2. Serum B 12	
	3. Serum Retinol	
	4. Serum backup	
	5. Serum Fe, sTfR, CRP, AGP, and	
	RBP	

Table 3: Shows details of sample collection, parameters to be tested and storage conditions at NPL

Note: All samples for tests to be performed in batches on frozen samples will be transferred to -70° C deep freezers after the samples reach TFNC.

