Vacutainers	and the frozen gel packs so that they do not touch. There will be 2 purple
	top vacutainers and one yellow top vacutainer. All the specimens in the cold
	box and the portable freezer must be sent at the end of the day for
	processing and storage.
	The Lab Technicians should keep the cold box closed at all times. Avoid
	leaving the lid open and exposure to direct sun. A digital thermometer will
Cold Boxes	be included in each cold box. The temperature of the cold box should
	remain $<8^{\circ}$ C. When temperature of the cold box reaches $\sim6^{\circ}$ C call the
	Supervisor to have a Driver deliver new frozen gel packs.
	The purple top vacutainer #1 for measuring: 1) Hemoglobin/CBC using the
Purple Top	automated hematology analyzer at MPL 2) Reticulocyte count at MPL if
Vacutainer#1	necessary. 3) DNA extraction for MTHFR. Extracted DNA will be stored in
	labeled Eppendorf tubes after completing the extraction procedure.
Purple Top	The purple top vacutainer #2 will be used to make 1) WBL for the Folate
Vacutainer#2	microbiological assay 2) Backup of WBL. Then the vacutainer will be spun

17 Annexure 2: Cold Chain Logistics

	down in the centrifuge for 3) Plasma HCY 4) Back up vial for Plasma.
Yellow Top Vacutainer	The yellow top vacutainer needs to be spun down for serum using the centrifuge and then aliquoted into 4 cryovials and 1 PCR vial for 1) Serum Folate, 2) Serum B12, 3) Serum Retinol, 4) Back-up vial for serum, 5) PCR vial for Ferritin, sTfR, CRP, AGP, RBP

19 Four teams will collect 21 samples from each village, $n = 21$						
	21 households per village (plus extra supplies)					
Supply Item	Quantity Required					
Backpack	4					
Yellow Top Vacutainers	25 per team= 50 per day					
Purple Top Vacutainers	50 per team= 100 per day					
Tourniquet	2 per team= 4 (can be reused)					
21G Needles	25 per team= 50 per day					
Vacutainer Barrels	4 per team (can be reused)					
Sharps container	1 Box each= 2					
Alcohol pads	30 per team= 60 per day					
Gauze pads	30 per team= 60 per day					
Absorbent pads	2 (can be reused if clean)					
Biohazard bags	2					
Ziploc bags	15 small per team= 30 per day					
Labels	3 sets pre-printed per subject= 25 sets					
Cold box	1 per team= 2					
Frozen Gel Packs	4-5 for each cold box= 10					
Bubble Wrap	2Large Piece (to protect specimens from frozen gel packs inside each cold box)					
	1 each for cold box $=2$					
Digital Thermometer						
Vacutainer Rack for						
Cold Box	1 each per box					

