ANNEX 6: PROCEDURE FOR VENOUS BLOOD COLLECTION

The lab technician will be responsible for performing venipuncture on all participants at the household. After obtaining consent, the Nurse will be given only two chances to collect blood from each participant.

- I. Always remember to practice Universal Precautions
 - 1. Assume that all human blood is potentially infectious for HIV, HBV, and other infectious agents.
 - 2. Use gloves and any additional personal protective equipment (PPE) if available (e.g., eye protection, lab coats)
 - 3. Always use sterile, single-use disposable supplies for sample collection.

II. Preparing for venipuncture

- 1. Obtain informed consent for blood collection
- 2. Lay out a clean disposable absorbent pad on a table at the central field laboratory
- 3. Lay out all blood collection supplies and necessary labels. Assemble needle or butterfly needle into Vacutainer holder being sure that it is firmly seated into threads.
- 4. Loosely place Vacutainer tube into holder, but do not puncture top
- 5. For each participant, wear a new pair of clean gloves and conduct all procedures on a new, clean disposable absorbent pad

III. Venipuncture Procedure

- 1. Check the ID bracelet against remaining lab labels
- 2. Make sure the participant is sitting comfortably.
- 3. Examine both arms to find the best vein.
- 4. Locate the puncture site and apply the tourniquet
- 5. Cleanse the area with an alcohol wipe by wiping in a circular motion making sure the area is thoroughly cleaned
- 6. Repeat with a second wipe, if necessary

- 7. Dry with gauze
- 8. Fix the vein by pressing down on the vein about 1 inch below the proposed point of entry
- 9. Remove the butterfly needle shield
- 10. Approach the vein in the same direction the vein is running, holding the needle so that it is at an approximately 15° angle with the participant's arm.
- 11. Push the needle, with the bevel facing up, firmly and deliberately into the vein.
- 12. Activate the vacuum collection tube by pushing the tube onto the needle and puncturing the tube top.

- 13. If the needle is in the vein, blood will flow freely into the tube.
- 14. If no blood enters the tube, probe for the vein once or twice until entry is indicated by blood flowing into the tube.
- 15. After blood flow is established, loosen the tourniquet immediately and release entirely as the last tube fills.

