PROCEDURES

I. Preparing for venipuncture

- 1. Obtain informed consent for blood collection
- 2. Lay out a clean disposable absorbent pad on a table/ chair available at the house hold
- 3. Lay out all blood collection supplies and necessary labels. Assemble needle or butterfly needle into Vacutainer holder being sure that it is firmly seated into threads.
- 4. Loosely place Vacutainer tube into holder, but do not puncture top
- 5. Wear a new pair of clean gloves and conduct all procedures on a new, clean disposable absorbent pad

II. Venipuncture Procedure

[figure not shown]
- 1. Check the participant ID against remaining lab labels
- 2. Make sure the participant is sitting comfortably.
- 3. Examine both arms to find the best vein.
- 4. Locate the puncture site and apply the tourniquet.
- 5. Cleanse the area with an alcohol wipe by wiping in a circular motion making sure the area is thoroughly cleaned.
- 6. Repeat with a second wipe, if necessary
- 7. Dry with gauze.
- 8. Fix the vein by pressing down on the vein about 1 inch below the proposed point of entry.
- 9. Remove the butterfly needle shield.
- 10. Approach the vein in the same direction the vein is running, holding the needle so that it is at an approximately 15° angle with the participant's arm.
- 11. Push the needle, with the bevel facing up, firmly and deliberately into the vein.

- 12. Activate the vacuum collection tube by pushing the tube onto the needle and puncturing the tube top.
- 13. If the needle is in the vein, blood will flow freely into the tube.
- 14. If no blood enters the tube, probe for the vein once or twice until entry is indicated by blood flowing into the tube.
- 15. After blood flow is established, loosen the tourniquet immediately and release entirely as the last tube fills.
- 16. Fill one yellow top vacutainer with 4 ml of blood and fill 2 Purple Top Vacutainer with 4 ml of blood.
- 17. Upon completion of blood collection, withdraw the needle. Applying heavy pressure as the needle is being withdrawn should be avoided.
- 18. Have the mother/caregiver continue to hold the gauze in place for several minutes. This will help prevent hematomas.
- 19. Invert the Purple Top Vacutainer 10 times after blood collection so that the blood will mix with the EDTA in the tube to prevent clotting. Gently invert the Blue Top Vacutainer 5 times after blood collection to mix with clot activator.
- 20. Place an adhesive bandage on the participant's arm.

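### Annexure 3 stocks two reusable absorbent pads for a 21-woman village, but Annex 6 requires a new pad for every participant

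*Protocol*

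**What the plan says.** All the texts are in Protocol section 8.3.

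- **Annexure 3 (daily supplies), absorbent-pad row:** "2 (can be reused if clean"). The row has no per-team multiplier. The list is headed for "21 households per village (plus extra supplies").
- **Status of the list:** the text on items to take to the field says "Complete list of supplies to be taken by each team for specimen collection of 21 women is given in Annexure 3".
- **Annex 6, part II, step 5:** "For each participant, wear a new pair of clean gloves and conduct all procedures on a new, clean disposable absorbent pad". Part I, step 1 of the same annex sets the premise: "Assume that all human blood is potentially infectious for HIV, HBV, and other infectious agents". Part I, step 3 asks for single-use disposables throughout sample collection.
- **Venous-blood SOP, preparation step 5:** "Wear a new pair of clean gloves and conduct all procedures on a new, clean disposable absorbent pad". It has the same content as Annex 6 but does not say that the pad is changed for each participant.
- **Other rows of Annexure 3:** alcohol pads and gauze pads are each listed as "30 per team= 60 per day", needles at 25 per team, and gloves at a minimum of 30 pairs per team. Tourniquets and vacutainer barrels are marked as reusable.
- **Laboratory personnel's duties:** supplies each day must cover 21 draws plus 10%.

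**The concern.** Annex 6 makes the pad a single-use item, and the packing list treats it as reusable. The conflict lies in the wording, so it does not depend on any count: a pad that has been used and is still clean satisfies Annexure 3 but is not new, and so fails Annex 6. The count then makes Annex 6 impossible to follow for anyone who packs from the list.

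The pad is the surface on which the blood-collection supplies are laid out and the venipuncture is done. Blood is drawn in each woman's household, so a reused pad would travel from one home to the next. What is at stake is a basic infection-control precaution and whether field staff have one clear instruction. No prevalence estimate, precision figure or sample-size figure is involved.

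**Working it through.** **Inputs**

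- Pads stocked: 2 (Annexure 3).
- Pads required: 1 new pad per participant (Annex 6, II.5).
- Women per village: 21 (heading of Annexure 3). Section 4.4 plans 26 households, one woman each, per enumeration area (EA), with 45 EAs.
- Reserve: 10% (laboratory personnel's duties).
- Number of teams: the appendix gives three answers. The introduction says "There will be one survey team, consisting of one supervisor, four interviewers, and four lab technicians", the totals in Annexure 3 (for example "30 per team= 60 per day") imply two teams, and the list's heading says four.

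**Can the listed figure be reproduced?** Required pads = 21 × 1 = 21. The listed 2 cannot be obtained under a rule of one new pad per woman. It would fit one reusable pad for each of two teams.

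**Women without a new pad** = (women − pads) / women

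| Reading of the row | Pads | Of 21 women | Of 26 women |
|---|---|---|---|
| 2 in total, or 2 per team with one team | 2 | 19 (90%) | 24 (92%) |
| 2 per team, two teams sharing the village | 4 | 17 (81%) | 22 (85%) |
| 2 per team, four teams sharing the village | 8 | 13 (62%) | 18 (69%) |

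The second and third rows keep the number of women fixed, as the list's heading does when it has four teams collect 21 samples per village. If each of two teams drew blood from 21 women of its own, the denominator would be 42: 4 pads would leave 38/42 (90%) without a new pad, and 2 pads would leave 40/42 (95%). The stock falls short on every reading.

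**Stock that would satisfy Annex 6 with the 10% reserve**

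- 21 × 1.10 = 23.1, rounded up to 24 per village.
- 26 × 1.10 = 28.6, rounded up to 29 per EA.
- Whole survey: 29 × 45 = 1,305, against 2 × 45 = 90 on the literal row, a difference of 1,215.

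**The case against.** The strongest reply is that a packing list is not a rule for drawing blood. Every procedural text points the same way: Annex 6 asks for a new pad, the SOP asks for a new pad and is signed by staff, Annexure 1 sends used materials to biohazard bags, and the personnel duties require enough supplies for 21 draws plus 10%. On this view staff would follow the procedure and bring more pads. This softens the gap but does not close it. A general duty to carry enough does not cancel a row that expressly allows reuse, in a list the appendix calls complete.

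A second reply is that the row may refer to a different pad. Annex 6, II.2 has a clean disposable pad laid on the table before II.5 asks for a new one per participant, so the 2 could be table pads. If so, the per-participant pads are missing from the list altogether. The defect changes in kind, but the same row needs correcting.

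Two further points stand. First, 19 of 21 is the literal figure, not the only one, because the appendix is inconsistent about the number of teams. Second, the matter is operational and slight beside the appendix's larger conflicts with section 4.4, such as 55 villages of 21 households against 45 EAs of 26. Both limit its weight, and neither reconciles the two instructions.

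**Conclusion.** The contradiction is real. Annexure 3 permits reuse of an item that Annex 6 requires to be new for each woman, and it stocks too few on any reading: 19 of 21 women without a new pad literally, and 13 of 21 on the most favourable reading. The conflict of wording rests on no assumption. The size depends on how many teams the row covers and on whether they share the 21 women.

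The severity is minor. The women would lack a new pad, not any pad. Reuse is conditional on the pad being clean, the other per-draw items are adequately stocked, and the Protocol gives no evidence of carry-over between participants. Nothing in the survey's design, estimates or analysis changes.

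**What to change.** Before fieldwork:

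1. In the absorbent-pad row of Annexure 3, delete the permission to reuse and list one pad per draw plus 10%: 24 for a village of 21, or 29 for an EA of 26 if the list is brought into line with section 4.4.
2. In preparation step 5 of the venous-blood SOP, state that the new pad is for each participant, so that it matches Annex 6, II.5.

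This is one list row and one SOP step, with no extra staff or procedure. The 1,305 pads for 45 EAs are a ceiling that assumes blood is drawn in all 26 households; section 4.2 plans on a response rate of 68%. Section 4.5 adds 2 to 4 pilot EAs. If those were also full size, the total would be 29 × 47 = 1,363 to 29 × 49 = 1,421.

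The Protocol gives no unit price. At an assumed $0.05 to $0.50 per pad, the range runs from 1,305 × $0.05 = $65 to 1,421 × $0.50 = $711, about 0.2% to 1.6% of the $43,106 disposable-supplies line in section 6.

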ANNEX 6: PROCEDURE FOR VENOUS BLOOD COLLECTION

The lab technician will be responsible for performing venipuncture on all participants at the household. After obtaining consent, the Nurse will be given only two chances to collect blood from each participant.

- I. Always remember to practice Universal Precautions
 - 1. Assume that all human blood is potentially infectious for HIV, HBV, and other infectious agents.
 - 2. Use gloves and any additional personal protective equipment (PPE) if available (e.g., eye protection, lab coats)
 - 3. Always use sterile, single-use disposable supplies for sample collection.

II. Preparing for venipuncture

- 1. Obtain informed consent for blood collection
- 2. Lay out a clean disposable absorbent pad on a table at the central field laboratory
- 3. Lay out all blood collection supplies and necessary labels. Assemble needle or butterfly needle into Vacutainer holder being sure that it is firmly seated into threads.
- 4. Loosely place Vacutainer tube into holder, but do not puncture top
- 5. For each participant, wear a new pair of clean gloves and conduct all procedures on a new, clean disposable absorbent pad

III. Venipuncture Procedure

- 1. Check the ID bracelet against remaining lab labels
- 2. Make sure the participant is sitting comfortably.
- 3. Examine both arms to find the best vein.
- 4. Locate the puncture site and apply the tourniquet
- 5. Cleanse the area with an alcohol wipe by wiping in a circular motion making sure the area is thoroughly cleaned
- 6. Repeat with a second wipe, if necessary

- 7. Dry with gauze
- 8. Fix the vein by pressing down on the vein about 1 inch below the proposed point of entry
- 9. Remove the butterfly needle shield
- 10. Approach the vein in the same direction the vein is running, holding the needle so that it is at an approximately 15° angle with the participant's arm.
- 11. Push the needle, with the bevel facing up, firmly and deliberately into the vein.
- 12. Activate the vacuum collection tube by pushing the tube onto the needle and puncturing the tube top.

- 13. If the needle is in the vein, blood will flow freely into the tube.
- 14. If no blood enters the tube, probe for the vein once or twice until entry is indicated by blood flowing into the tube.
- 15. After blood flow is established, loosen the tourniquet immediately and release entirely as the last tube fills.
- 16. For all participants, fill one yellow top vacutainer with 6 ml of blood and fill 2 Purple Top Vacutainer with 3 ml of blood

Yellow top	Purple top 1	Purple top 2
6 ml	3 ml	3 ml

[figure not shown]
- 17. Upon completion of blood collection, withdraw the needle. Applying heavy pressure as the needle is being withdrawn should be avoided.
- 18. Have the mother/caregiver continue to hold the gauze in place for several minutes. This will help prevent hematomas.
- 19. Invert the Purple Top Vacutainer 10 times after blood collection so that the blood will mix with the EDTA in the tube to prevent clotting. Gently invert the Blue Top Vacutainer 5 times after blood collection to mix with clot activator
- 20. Place an adhesive bandage on the participant's arm
- 21. Label all tubes with the correct and corresponding labels provided (i.e. "Purple Top Vac1" or "Purple top vac 2" or "yellow top vac")
- 22. Place the correct corresponding "Specimen Ctrl" label on the "Biological Specimen Control Form" (Annexure 7) and complete the necessary information
- 23. The needle should be discarded into a sharps container.

- 24. Place **labeled tubes** into a rack inside a cold box with frozen gel packs and discard waste into a biohazard bag.
- 25. Report to the team leader/supervisor any reaction experienced by the participant during the venipuncture procedure

Annexure 7 - Specimen Control Form

BIOLOGICAL SPECIM				HH BIOMA	KKERS CO	DLLECTIC)N			
**Complete all section	is. De sure to sign (.0111/01 10	nn each day							
GENERAL INFORMAT	TION									
District:		Date			I .					
		Date	Day	Month	Ye	ar				
Village:										
Place labels for all wo	men in blocks prov	ided belo	ow Vacutainer (P)	Vac	utainer (P)		Vacutainer (Y)			
Total number of WRA	samples collected			Vac					1	
		- H								
Phlebotomist Name		Phlehot	tomist Signature	•						
SPECIMEN COLLECT		s, AND TI	EMPERATURE	MONITORI	IG FOR CO	JLD BOX				
nstructions for Phleb .) Record the time froze	л	l into the c	old boy in the mo	rning						
2.) Place each WRA's lab					as collected	l and/or te	st was performed	1.		
3.) Record temperature o										
l.) Replace thawing gel µ										
ime frozen gel pack	s placed into the co	old box in	n the morning							
		 							Time	Box #
						nen vials	check (x)	Volume	Processed	
	Specimen T	vpe	NPL- pro	cessing	Serum Fol			-		
					Serum B12	. ,		-		
			CBC		Serum Fer		9	-		
	Vacutainer (P)		WBL		Serum TfR					
	Vacutainer (P)		PLASMA		Serum CR					
	Vacutainer (Y)		SERUM		Serum Ext			-		
					Plasma HC			-		
			Taman		Plasma Ext WBL Folate			-		
	Temp:		Temp		WBL extra					
					MEL CAU	(000 01)				
		 							Time	Box #
		i i i i			Specim	nen vials	check (x)	Volume	Processed	
	Specimen T	vne	NPL- pro	cessina	Serum Fol			-		
		152		oo comq	Serum B12	2 (500ul)		_		
			CBC		Serum Fer	ritin (500u	Ŋ	-		
2	Vacutainer (P)		WBL		Serum TfR	(500ul)			1	
	Vacutainer (P)		PLASMA		Serum CR	P (write ul)				
	Vacutainer (Y)		SERUM		Serum Ext	ra (write ul)		-		
					Plasm a HC			-		
		 			Plasma Ext			-		
	Temp:		Temp		WBL Folate	. ,				
					WBL extra	(500 ui)				
									Time	Box #
		1 H			Specim	nen vials	check (x)	Volume	Processed	
	Specimen T	vpe	NPL- pro	cessing	Serum Fol	ate (500ul)		-		
					Serum B12	2 (500ul)		-		
			CBC		Serum Fer		り	-		
3	Vacutainer (P)		WBL		Serum TfR					
	Vacutainer (P)		PLASMA		Serum CR					
	Vacutainer (Y)	┡━━┦	SERUM		Serum Ext		_	-		
		┢──┤			Plasma HC Plasma Evi			-		
_ _	Tomn	┢──┤	Tomp		Plasma Ext WBL Folate			-		
	Temp:		Temp		WBL extra		_			

Annexure 8: Flow Chart for specimen field collection and processing at MPL

Part II – Standard Operating Procedures

Standard Operating Procedure (SOP) - Venous Blood Collection

TANZANIA FOOD AND NUTRITION CENTRE MICROBIOLOGY LABORATORY SECTION Study Specific Standard Operating Procedure (SOP) for Venous Blood Collection TANZANIA FOOD AND NUTRITION CENTRE Version No: Copy no. Prepared by: 1. 2. Authorized by:

Changes:

0			
 •••••••••••••••	 		

Reasons for changes:

	0		
•••••			
SCODE			

SCOPE

Applied during venous blood sample collection for survey of micronutrients biomarker study

PURPOSE

• To ensure proper technique during vein puncture and blood sample collection

RESPONSIBILITIES

1. The phlebotomies will be responsible for performing venipuncture on all participants at the field.

2. All personnel (Nurses, Laboratory technologist) involved in the study should be trained and follow this SOP during field sample collection at the households.

PRINCIPLE

Venous blood sample is collected from the vein by pressing down on the vein about 1 inch below the proposed point of entry. A tourniquet is applied after location the puncture site and the blood sample is filled into the vacutainer tubes.

ABBREVIATIONS

EDTA Ethylene diamine tetra-acetic acid ID Identification

Materials needed:

- Vacutainers
- Specimen labels with barcode
- Marker pen
- Absorbent pad
- Gauze

PROCEDURES

I. Preparing for venipuncture

- 1. Obtain informed consent for blood collection
- 2. Lay out a clean disposable absorbent pad on a table/ chair available at the house hold
- 3. Lay out all blood collection supplies and necessary labels. Assemble needle or butterfly needle into Vacutainer holder being sure that it is firmly seated into threads.
- 4. Loosely place Vacutainer tube into holder, but do not puncture top
- 5. Wear a new pair of clean gloves and conduct all procedures on a new, clean disposable absorbent pad

II. Venipuncture Procedure

[figure not shown]
- 1. Check the participant ID against remaining lab labels
- 2. Make sure the participant is sitting comfortably.
- 3. Examine both arms to find the best vein.
- 4. Locate the puncture site and apply the tourniquet.
- 5. Cleanse the area with an alcohol wipe by wiping in a circular motion making sure the area is thoroughly cleaned.
- 6. Repeat with a second wipe, if necessary
- 7. Dry with gauze.
- 8. Fix the vein by pressing down on the vein about 1 inch below the proposed point of entry.
- 9. Remove the butterfly needle shield.
- 10. Approach the vein in the same direction the vein is running, holding the needle so that it is at an approximately 15° angle with the participant's arm.
- 11. Push the needle, with the bevel facing up, firmly and deliberately into the vein.

- 12. Activate the vacuum collection tube by pushing the tube onto the needle and puncturing the tube top.
- 13. If the needle is in the vein, blood will flow freely into the tube.
- 14. If no blood enters the tube, probe for the vein once or twice until entry is indicated by blood flowing into the tube.
- 15. After blood flow is established, loosen the tourniquet immediately and release entirely as the last tube fills.
- 16. Fill one yellow top vacutainer with 4 ml of blood and fill 2 Purple Top Vacutainer with 4 ml of blood.
- 17. Upon completion of blood collection, withdraw the needle. Applying heavy pressure as the needle is being withdrawn should be avoided.
- 18. Have the mother/caregiver continue to hold the gauze in place for several minutes. This will help prevent hematomas.
- 19. Invert the Purple Top Vacutainer 10 times after blood collection so that the blood will mix with the EDTA in the tube to prevent clotting. Gently invert the Blue Top Vacutainer 5 times after blood collection to mix with clot activator.
- 20. Place an adhesive bandage on the participant's arm.
- 21. Label all tubes with the correct and corresponding labels provided (i.e "Purple Top Vac1" or "Purple top vac 2" or "yellow top vac").
- 22. Place the correct corresponding "Specimen Ctrl" label on the "Biological Specimen Control Form" and complete the necessary information.
- 23. The needle should be discarded into a sharps container.
- 24. Place labeled tubes into a rack inside a cold box with frozen gel packs and discard waste into a biohazard bag.
- 25. Report to the team leader/supervisor any reaction experienced by the participant during the venipuncture procedure

I have read, understood and agreed to follow the procedure as documented

No.	Name	Signature	Date

Standard Operating Procedure (SOP) – for operating Sysmex XP 300 Hematology Analyzer

TANZANIA FOOD AND NUTRITION CENTRE-

Version No:		Copy no.	
Prepared by:			
Reviewed by:	1. 2.		
Authorized by:			

Changes:

	U																						
• • • • • •			• • • • •			• • • • • •			• • • • • •		• • • • • •						• • • • • •						
•••••	• • • • •	••••	•••••	•••••	•••••	•••••	•••••	•••••	•••••	•••••	•••••	• • • • • • •	•••••	• • • • • • •	•••••	• • • • • • •	•••••	•••••	••••	• • • • • • •	•••••	•••••	
•••••	••••	••••	•••••	•••••	•••••	•••••	•••••	•••••	•••••	•••••	•••												

Reasons for changes:

0	
***************************************	• • • • • • • • • • • • • • • • • • • •

SCOPE

This procedure describes the test method (automated) used for whole blood analysis (Full Blood Count - FBC) using the Sysmex XP 300 Hematology Analyzer. For the study titled: "Morogoro Region Micronutrient Household and Biomarker Survey, Tanzania, 2019"

PURPOSE

To ensure proper analysis and reporting of complete blood cell count with Sysmex XP 300 Hematology Analyzer

RESPONSIBILITIES

Laboratory Scientist/ technologist/ technicians involved in the study should be trained and follow this SOP during sample analysis

PRINCIPLE

The Sysmex XP 300 utilizes technology of fluorescence flow. The combination of side scatter (inner complexity of the cell), forward scatter (volume) and fluorescence intensity of nucleated cells gives a concise but precise image of each cell detected in the peripheral blood. A well-defined physical description of the different leucocyte populations (clusters) is obtained. Abnormal and immature cells, with their larger nuclear volume show much higher fluorescence intensity than normal cells, and are easily distinguishable in the DIFF scattergram.

Materials needed:

CellPack Stromatolyser Sulfolyser CellClean (detergent

PROCEDURES

Equipment startup

- 1. Check priority to operation such as reagents check, printer paper, instrument, sampler and waste fluid
- 2. Turn on the instrument by pressing power button
- 3. Turn on the IPU power ON, window system will start automatic
- 4. Log on window will appears, log on with user name and password provided
- 5. After successful log in equipment will perform self-test and temperature stabilization for 30minutes
- 6. After temperature stabilization equipment will perform background check for maximum of 3 minutes

Quality control procedures:

1. At the beginning of each work shift, all parameters are tested with blood control.

- 2. The 3 levels include: Abnormal Low, Normal, Abnormal High
- 3. Controls are stored at 2-8°C and brought to room temperature on a roller mixer before use.
- 4. Controls are gently inverted eight times according to the manufacturer's instruction before use.
- 5. From the RUN screen, press [SPECIMEN TYPE].

6. Use the arrow key on the keyboard to move the cursor to the appropriate QC file (i.e., low, normal or high) and press the [QC SPECIMEN] key.

9. Control values must be within three standard deviations, otherwise the measurement has to be repeated, if the control still out of range:

a. Check operation of the machine, ensuring it is clean and that all required supplies are present in sufficient quantities.

b. Check reagents for expiration dates and lot numbers. Ensure that all machine lines are in appropriate receptacle where applicable, If this does not solve the problem:

•Prepare new control(s) and try again.

•If the controls are still out, inform your supervisor to check the operator's manual, or recalibrate instrument and If controls are still out. Contact Medical Maintenance where applicable, or servicing engineer.

7. All control data are managed using software that provides graphical reports (Levey-Jennings graphs, and monthly cumulative histograms).

Run Samples

1. Check to see that the reagents needed for the number of the samples to be processed for the day are available.

[figure not shown]
2. Turn ON the power switch on the right side of the unit. Self-check, auto rinse, and background check will be automatically performed, and the "Ready" (ready for analysis) will appear.

3. When auto rinse and background check are normally completed, "Ready" is displayed.

4. Perform quality control analysis on 3 levels of control blood material (low, normal and high) to verify that the instrument is performing within the specified ranges of the quality control material.

5. If the result of quality control in acceptable range input your blood samples.

- 6. Input from the panel keyboard.
- 7. Press [SAMPLE No.] key in the Ready status.
- 8. Entering patient ID, sample ID, Patient name, etc
- 9. Press [ENTER] key, This will fix the sample No. and the status becomes ready for analysis.
- 10. Mix the sample sufficiently before analysis.
- 11. Remove the plug while taking care not to allow blood scatter.
- 12. Set the tube to the sample probe, and in that condition, press the start switch.
- 13. when the LCD screen displays "Analyzing," remove the tube.
- 14. After that, the unit executes automatic analysis and displays the result on the LCD screen.
- 15. Then the unit turns to the ready status, becoming ready for analysis of the next sample

TANZANIA FOOD AND NUTRITION CENTRE

Name:	Age/Sex:	F	Date:
Identification No.:			
Lab. No.:			
Address:			
Mobile No.:			
Investigation done: complete bloc	od cell count		

Report:

(attach results printout)

Interpretations:

Comments:

.....

Reported by

Reviewed by

Reference

Sysmex XP300 System Operator's Manual.

I have read, understood and agreed to follow the procedure as documented.

No.	Name	Signature	Date

Standard Operating Procedure for specimen collection/processing/shipment for RBC and serum folate assay

TANZANIA FOOD AND NUTRITION CENTRE

MICROBIOLOGY LABORATORY SECTION

Standard Operating Procedure (SOP) for specimen collection/processing/shipment for RBC and serum folate assay

TANZ ANIA FOOD AND NUTRITION CENTRE Version No: Copy no. Prepared by: Copy no. Reviewed by: 1. 2. Authorized by:

Changes:

-				
			•••••••••••••••••••••••••••••••••••••••	•••••
••••••	•••••••••••••••••••••••••••••••	•••••		

Reasons for changes:

•••••••••••••••••••••••••••••••••••••••	• • • • • • • • • • • • • • • • • • • •
	,
••••••	

SCOPE

This SOP describes the procedures for specimen collection/processing/shipment of red blood cell folate (Fol) for the study titled: Morogoro Regional Micronutrient Household and Biomarker Survey, Tanzania, 2019.

PURPOSE

• To ensure proper procedures for specimen collection/processing/shipment of red blood cell folate (Fol) for the study

RESPONSIBILITIES

Laboratory technologist/technicians involved in the study should be trained and follow this SOP during field sample collection and processing at the laboratory.

PRINCIPLE

Use of a consistently executed protocol for specimen collection and processing is essential, to eliminate data variability caused by erratic technique. Proper use of the pipette is a must as this ensures accuracy of the red blood cell (RBC) folate level. A hematocrit result is needed to calculate RBC folate from whole blood folate and needs to be obtained for each patient and communicated to the laboratory who analyzes the whole blood folate.

ABBREVIATIONS

EDTA Ethylene diamine tetra-acetic acid ID Identification

Materials needed:

- Usual blood collection supplies
- 4-mL K2EDTA Vacutainers
- Specimen labels with barcode
- 2-mL cryovials containing 1 mL of 1 g/dL ascorbic acid diluent (1% w/v); prepared ahead of time and stored frozen at -70°C for up to 6 months
- Alternatively: L-Ascorbic acid can be pre-weighed into 50-mL Falcon tubes (0.3 g/tube) and the tubes can be stored at room temperature, protected from light, for up to 1 year. The ascorbic acid solution (1% w/v) can be prepared freshly on a daily basis, as needed, by adding 30 mL of deionized water to the Falcon tube. Any left-over ascorbic acid solution should be discarded at the end of the day.
- 100-µL micropipet and disposable tips (to add EDTA whole blood to ascorbic acid vial for lysis of erythrocytes)
- White cardboard storage boxes, 9x9 array
- Marker pen
- Styrofoam insulated shippers
- Dry ice
- Cold packs
- Package sealing tape (clear type, such as 3M, preferred

PROCEDURES

I. Collection:

1. Follow standard venipuncture collection technique (SOP for Venous Blood Collection) to collect a 6 mL EDTA Vacutainer (spray-dried K2EDTA is preferred).

- 2. Mix the EDTA Vacutainer well by inversion at least 5 times after collection to ensure thorough mixing of the anticoagulant with the blood.
- 3. Place the EDTA Vacutainer into a coolbox that contains cold packs to keep it cool and protected from light during transport back to the laboratory.
- 4. Make sure though that you separate the Vacutainer from the cold packs through some paper to avoid unintentional hemolysis of red cells.
- 5. Discard the blood collection supplies properly in accordance with hospital regulations.

II. Processing:

